3.1 Background

A spinal cord injury (SCI) often leads to paralysis of respiratory muscles (1), which causes a decrease in inspiratory volume and consequently limits the pre-cough volumes needed to produce an effective cough (2). The ability to cough is essential for airway clearance (3). With reduced cough capacity, the risk for pneumonia is increased (1). Pneumonia is still among the leading causes of death in the SCI population (4, 5). In acute SCI, up to 80% of patients are affected by respiratory complications (6) and in 51% of these cases pneumonia occurs (7), corresponding to a cumulative pneumonia incidence rate of about 40%. Unfortunately, predictors of pneumonia in SCI are still poorly understood (6).

To our knowledge, there are three studies on predictors of pneumonia in the SCI population (8, 9). Two of these studies concentrated on factors of injury and shock severity (9) or identified the level and completeness of injury as the fundamental clinical entity predicting pulmonary complications (8). However, both studies did not investigate potentially modifiable factors. The third study focused on potentially modifiable factors, such as lung function but did not cover respiratory muscle strength and did not define the inclusion of respiratory complications precisely (10). Therefore, to facilitate future evidence-based strategies to reduce the pneumonia risk in acute SCI, prevention targeted studies that aim to identify modifiable risk factors for pneumonia are urgently needed.

The current research proposal is targeted at specific parameters of respiratory function that are conceivably determinants of pneumonia risk as well as modifiable by respiratory muscle training (11, 12). In a recent study (accepted for Publication, Respiratory Care) we evaluated various respiratory function parameters and identified inspiratory muscle strength as a reliable discriminator between individuals with and those without pneumonia.

Although we identified inspiratory muscle strength as best parameter of respiratory function to discover individuals with SCI at risk for pneumonia, these data are based on a retrospective singlecenter data analysis without any detailed information on the type, time-point and severity of pneumonia. Also data on mortality due to pneumonia and other personal parameters that may influence the risk for pneumonia as well (e.g. smoking, exercise, mechanical ventilation dependency etc.) are missing in this analysis.

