4.2 Primary and secondary endpoint/outcome(s) (STROBE #7)

Primary endpoint: Inspiratory muscle strength in relation to pneumonia

Secondary endpoints:

- mortality due to pneumonia
- quality of life
- other respiratory function parameters

Potential explanatory variables:

- personal and lesion characteristics (gender, age, height, weight, lesion level, AIS grade etc.)
- smoking status
- partly mechanical ventilation dependency
- medication and vaccination
- respiratory muscle training and physical exercise

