5.3 Recruitment and Screening (swissethics 3b)

During a consecutive enrollment all patients, who fulfill the inclusion criteria, will be asked for participation by a skilled study nurse.

Screening tests:

- demographic data (age, language)
- severity and level of the lesion
- exclusion criteria

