6.1 Inclusion criteria

Initial rehabilitation after SCI, men and women, age ≥ 18 years, AIS A, B, C or D lesion, lesion level C1-T12

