To evaluate the diagnostic accuracy of markers of lung function (particularly MIP) for predicting or excluding clinical pneumonia we will use contemporary receiver operating characteristic (ROC) analyses techniques that allow for adjusting of covariate effects (21). Such adjustments principally facilitate an unbiased estimate of pneumonia classification accuracy of potential marker(s) by controlling for the effects of other factors, such as for instance individual patient characteristics, disease traits, or site-specific features of measurement or diagnostic procedures. In case covariates affect discrimination (i.e., the ROC curve), nonparametric and parametric estimators have been proposed and implemented as to combine marker and covariate information in describing the improvement in discriminatory accuracy (21-23). Importantly, these methodologies thus also support the evaluation of adjusted ROC curves by individual patient characteristics (e.g., gender, age) or SCI characteristics (e.g., lesion level, lesion completeness, temporary or permanent artificial ventilation).

Regression modelling of secondary outcomes

Analyses of secondary outcomes will make use of common regression models, or extensions of these models. The choice of regression model will be determined by the statistical nature of the secondary outcome variable, in particular its error distribution (19). We thus anticipate using multiple regression for the modelling of the lung parameters MIP, MEP, FVC, FEV₁ and PEF, if needed using appropriate transformations as to meet normality assumptions. In case a normal error distribution is not achieved,

the outcome variable will be converted into a ordinal variable with multinomial categorical outcomes using clinically-relevant cut-offs and analysed using ordinal regression or stereotype regression, the latter in case of failure to meet proportional odds assumptions (24-26). Alternatively, a binary cut-off combined with logistic regression analysis may be used.

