For the analysis of all-cause and pneumonia-related mortality flexible parametric survival models will be applied that allow for a flexible approach in modelling and estimation of the baseline hazard of death (27, 28). Survival time will start at the date of initiation of first rehabilitation and censoring is at date of discharge from local first rehabilitation or at date of death. The analysis of pneumonia-related mortality will be adjusted for competing risks, i.e., events that either hinder the observation of the event of interest or modifies the chance that this event occurs. Potential competing risks for the event of pneumonia-related mortality during first SCI rehabilitation for instance include other causes of mortality (e.g., septicaemia, neoplasm) or transfer to another rehabilitation clinic or another facility to receive specialized treatment. In such cases the censored time-to-events reflect a form of incomplete data that may induce bias in estimates of pneumonia risk from unadjusted analyses. Competing risk analysis accounts for competing events as to provide an unbiased estimate of the pneumonia-related hazard of death during first rehabilitation (29, 30).

Predictors; extraneous, mediating, moderating and confounding variables

The main predictors (exposures of interest) in the modelling of the primary outcome and secondary outcomes include the degree of motor and sensory neurological impairment as captured by the ASIA Impairment Scale (35); lesion level classified as paraplegia or tetraplegia; PCF and partial dependency on mechanical ventilation (a minimum of 1hour free of ventilator dependency during the day). Further predictors for secondary outcomes include an index of physical activity as well as an indicator for respiratory training, assessed using a questionnaire.

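### Lesion level is entered only as paraplegia or tetraplegia, so covariate-adjusted results for MIP may keep part of the lesion-level confounding; the unadjusted AUC and cut-off are not affected

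*Combined protocol and SAP*

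**What the plan says.** All references are to the combined protocol and SAP.

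- **Coding.** Section 8.3.2 (Advanced regression modelling), under predictors and confounders: "The main predictors (exposures of interest) in the modelling of the primary outcome and secondary outcomes include" AIS grade, "lesion level classified as paraplegia or tetraplegia", peak cough flow (PCF) and partial ventilator dependency.
- **Population.** Section 6.1 admits "AIS A, B, C or D lesion, lesion level C1-T12". That is 8 cervical and 12 thoracic segments.
- **Data.** Section 5.3 lists "severity and level of the lesion" among the screening items, and eligibility cannot be checked without the segment. Section 4.2 lists lesion level as an explanatory variable without saying how it is coded.
- **Purpose of adjustment.** Section 8.3.2, primary outcome, says that covariate adjustment of the ROC curve will "facilitate an unbiased estimate of pneumonia classification accuracy of potential marker(s) by controlling for the effects of other factors". It names lesion level as one such characteristic and gives no coding.
- **Flexible modelling.** Section 8.3.2 plans fractional polynomials and splines for continuous variables, with age and time since injury as examples. Lesion level is not mentioned there.
- **Elsewhere.** The section on datasets to be analysed uses the same two-group split for subgroups. The ancillary analyses contain no analysis by segment.

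**The concern.** The only coding the plan states treats C1 like C8 and T1 like T12. Section 3.1 reports a prior study that "identified the level and completeness of injury as the fundamental clinical entity predicting pulmonary complications", and it explains that SCI can paralyse the respiratory muscles and limit cough. Level is therefore a plausible common cause of low MIP and of pneumonia.

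If MIP and pneumonia risk still change with level inside each group, a patient with lower MIP within tetraplegia tends to have a higher lesion. The adjusted MIP estimate and the covariate-adjusted ROC curve then credit MIP with some of what belongs to level. Specific aim 1, which treats lesion characteristics as determinants of pneumonia, loses any gradient within the groups. A two-group variable also gives no means of checking whether such a gradient exists.

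**Working it through.** **Inputs from the documents.** 20 segments (8 cervical, 12 thoracic); 625 patients; 40% incidence. The plan gives no figure for the effect of the coding. The nearest figure is the number of cases, and it reproduces: 625 × 0.40 = 250.

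**Assumed inputs.** The documents give neither the distribution of levels nor the strength of the associations. I take a level-MIP correlation r of 0.3 to 0.7, a pneumonia OR of 1.5 to 3 per SD of level (log-odds b), no effect of MIP itself, and no other covariates.

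**Step 1: what the split keeps.** Number the levels C1 = 1 to T12 = 20 and let them be equally frequent. The group means are 4.5 and 14.5.
- Between-group variance: 0.4 × 0.6 × (14.5 − 4.5)² = 24.
- Total variance: (20² − 1)/12 = 33.25.
- Share kept: 24/33.25 = 0.72. Share left within groups: w = 0.278.

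Other assumed patterns (about half tetraplegic, levels clustered within groups, or a gradient in tetraplegia only) keep 71 to 82%, so w runs from 0.18 to 0.29.

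**Step 2: what remains in the MIP estimate.** On a linear approximation, the spurious log-OR per SD lower MIP is b·r without adjustment. After para/tetra adjustment it is b·r·w / (r²·w + 1 − r²). After adjustment for level it is 0. With w = 0.278:

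| r | OR per SD of level | Unadjusted OR | Para/tetra-adjusted log-OR | OR |
|---|---|---|---|---|
| 0.3 | 1.5 | exp(0.405 × 0.3) = 1.13 | 0.0338/0.935 = 0.036 | 1.04 |
| 0.5 | 2 | exp(0.693 × 0.5) = 1.41 | 0.0964/0.820 = 0.118 | 1.12 |
| 0.7 | 3 | exp(1.099 × 0.7) = 2.16 | 0.2139/0.646 = 0.331 | 1.39 |

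Logistic simulation at 40% pneumonia, with level mixes that keep 72 to 77% of the variance, gives about 1.03 to 1.35 after para/tetra adjustment and about 1.00 after ordered-level adjustment. The formula lies slightly above the simulation at the strong end because a logistic OR shrinks when part of the level effect is left out of the model.

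**Step 3: how much the split already removes.** In the middle case the simulated OR falls from 1.40 unadjusted to 1.12. The share left is ln 1.12 / ln 1.40 = 0.113/0.336 = 0.34, so about two thirds of the confounding is removed.

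**Step 4: adjusted AUC.** Take r of 0.3 to 0.7, b of 0.4 to 0.8 per SD of level (OR 1.49 to 2.23) and 40 to 60% tetraplegia. The para/tetra-adjusted AUC is 0.505 to 0.567 when the true adjusted value is 0.50, an excess of 0.005 to 0.067. Section 8.1 sizes the study for an AUC change of 0.07 to 0.05. Only the top of the range reaches that, and it needs r = 0.7 with the gradient confined to tetraplegia. These values are for a marker with no effect of its own. They show the scale and are not a correction to apply to an AUC near 0.86.

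**Step 5: the null case.** With no gradient inside either group, nothing remains: adjusted AUC 0.50 and OR 1.00.

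**The case against.** The strongest case on the other side has five parts.

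1. **The primary accuracy result is a prediction measure.** A reader might infer that the AUC and cut-off for MIP are biased. The documents do not support that. Section 4.1 asks how well cut-off levels predict pneumonia, and for that it does not matter whether MIP carries lesion-level information. This objection stands, and the point is confined to adjusted results.
2. **The plan does not say that the segment is thrown away.** A reader might infer that it does. Section 8.3.2 says the predictors include the two-group variable and lists it as an exposure of interest. The adjusted-ROC text names lesion level without a coding, and the final confounder strategy is left to a causal diagram. This stands in part. The two-group form is nonetheless the only one stated, and choosing covariates by diagram does not settle how they are coded.
3. **The gradient is not in the documents.** A reader might take it as the protocol's own premise that respiratory loss grows with every higher segment. Section 3.1 does not say so. The gradient is a plausible assumption, and without it there is no bias. This stands.
4. **Other covariates help.** AIS grade, PCF and partial ventilation sit in the same list. With equally frequent levels, r = 0.5 and level OR 2, adding an assumed PCF covariate (correlation with level 0.5 to 0.7) moves the OR only from 1.13 to 1.10 to 1.12. They may absorb some of the effect, but none of them replaces the level.
5. **The simulation favours ordered level.** Risk was made to depend on numeric level, so that adjustment is right by construction. This is true, and it is a reason to allow a flexible form.

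**Conclusion.** The point holds in a limited form. The plan's only stated coding is coarser than the recorded data, and it conflicts with the plan's own expectation of an unbiased estimate through adjustment. If MIP and pneumonia risk vary with level within tetraplegia or within paraplegia, part of the confounding stays in the covariate-adjusted ROC and the adjusted MIP estimates, and the estimate for lesion level itself is blunted.

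The size is unknown from the documents. Under the assumed inputs the spurious OR ranges from negligible (about 1.03) to material (about 1.35), and the two-group split already removes most of the confounding in the middle case. The change should be made because it is cheap and lets the data show whether a gradient exists. It does not call the study's validity into question.

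**What to change.** In section 8.3.2 (Advanced regression modelling), replace the two-group predictor by the recorded neurological level as an ordered numeric variable (C1 = 1 to T12 = 20). Model it with the fractional polynomial or spline approach already planned for continuous variables, and state that this coding applies to both the covariate-adjusted ROC analysis and the regression models. Keep paraplegia/tetraplegia for the descriptive tables and for the subgroup analyses already planned. No interaction with AIS grade is needed for this purpose.

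The cost is one or two sentences in the plan and about one to three extra degrees of freedom, against about 250 expected pneumonia cases. No new data collection is needed.

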5.2 Procedures (STROBE 5; swissethics 3a)

During inpatient rehabilitation 4 measurement time-points (T1-T4) will be used to assess longitudinal data of each participating patient.

Measurements:

- in- and expiratory muscle strength (5min)
- lung function (FVC, FEV1, PEF, PCF) (10min)

Questionnaires:

- ISCoS core data-set (5min)
- ISCoS pulmonary function data sets (5min)
- ISCoS quality of life questionnaire (5min)
- questionnaire on individual respiratory muscle training, regular physical exercise and therapies (5-10min)

Individual medication/vaccination and other medical complications will be assessed from patient's medical records.

All measurements will be performed at each measurement time-point and last about 40 min per patient and measurement time-point in total (time with patient).

For the study nurse time needed per patient and measurement time-point (including planning, preparation, documentation and data entry) will be about 90 min.

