7. PROJECT ASSESSMENTS

(STROBE 7; HRO Annex 2/1.2)

Project Periods	Screening				
Visit	Before T1	T1	T2	T3	T4
Time-frame in days post injury (PI)		28±12	84±14	150±18	10 day before discharge until discharge
Screening: In- /Exclusion Criteria	x				
Participant Information and Informed Consent	x				
Demographics		x			
Medical History/medication/mortality		x	x	x	x
Co-morbidities (ICD-10)					x
Questionnaires: - ISCoS core data set, pulmonary function data set and quality of life data set - questionnaire on individual respiratory muscle training, regular physical exercise and therapies		x	x	x	x
Tests: - in- and expiratory muscle strength - lung function (FVC, FEV1, PEF, PCF)		x	x	×	x

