7.1 Project flow chart(s) / table of procedures and assessments

7.2 Assessments of primary endpoint/outcome

The primary endpoint of this study is the diagnostic accuracy of inspiratory muscle strength for predicting or excluding clinical pneumonia. Diagnostic accuracy of positive and negative results will be evaluated by the area under the receiver operating characteristic (ROC) curve, which provides an operational measure of the intrinsic ability of the diagnostic test by offsetting the true positive rate against the false positive rate (13). Based on our previous evidence, MIP was defined as the primary diagnostic lung parameter (14). The potential additive diagnostic value of various other lung parameters, including forced vital capacity (FVC), forced expiratory volume in 1 second (FEV₁), peak expiratory flow (PEF), peak cough flow (PCF) and maximum expiratory muscle strength (MEP) will also be investigated. The two measures for the primary endpoint, maximal inspiratory pressure (MIP) and the event of clinical pneumonia, are assessed as follows.

Inspiratory muscle strength will be measured using a hand-held respiratory pressure meter (Micro RPM, Micro Medical, Hoechberg, Germany) by an independent study nurse of each participating study site. All measurements will be performed with the patients sitting upright in their own wheelchair. Patients have to breathe through a mouthpiece while wearing a nose clip. Each measurement will be repeated three times. The greatest value of each parameter will be used for analysis (15).

For each event of pneumonia the following information will be recorded: date of event; duration of event; physician diagnosed; and type. The differentiation of the type of pneumonia is important and will be evaluated using patients medical records data following the pneumonia flow diagram of "Disease and Control Prevention / National Healthcare Safety surveillance definition of health care—associated infection and criteria for specific types of infections in the acute care setting" (16). To determine the type of pneumonia the methods x-ray, signs and symptoms and the laboratory are used. Finally four different types of pneumonia can be diagnosed.

Pneumonia 1: clinically defined pneumonia

Pneumonia 2: pneumonia with common bacterial or filamentous fungal pathogens and specific lab findings

Pneumonia 3: pneumonia with viral and other uncommon pathogens and specific lab findings Pneumonia 4: pneumonia in immunocompromised patients

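### Peak cough flow is listed as a main predictor in models of the other same-visit lung parameters, on which it partly depends, and is given no model of its own; this would attenuate the lesion, ventilation and training effects on lung function

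*Combined protocol and SAP*

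**What the plan says.** In section 8.3.2 (Advanced regression modelling), the paragraph on predictors opens: "The main predictors (exposures of interest) in the modelling of the primary outcome and secondary outcomes include". The list that follows contains AIS grade, paraplegia or tetraplegia, and "PCF and partial dependency on mechanical ventilation (a minimum of 1hour free of ventilator dependency during the day". Physical activity and respiratory training are added as further predictors for secondary outcomes. No predictor set is given per outcome.

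Under the modelling of secondary outcomes, the same section says: "We thus anticipate using multiple regression for the modelling of the lung parameters MIP, MEP, FVC, FEV₁ and PEF". PCF is not among these outcomes.

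Elsewhere PCF is treated as a lung parameter. Section 7.2 places it with the other lung measures whose added diagnostic value is of interest: "peak cough flow (PCF) and maximum expiratory muscle strength (MEP) will also be investigated". Section 7.3 describes its measurement under the secondary endpoints. The assessment table in section 7 puts it in one test battery, "lung function (FVC, FEV1, PEF, PCF", at T1 to T4, and section 5.2 confirms the common timing: "All measurements will be performed at each measurement time-point and last about 40 min per patient".

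On mechanism, section 3.1 says that respiratory muscle paralysis "causes a decrease in inspiratory volume and consequently limits the pre-cough volumes needed to produce an effective cough".

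**The concern.** Taken together, these statements make PCF a regressor for MIP, MEP, FVC, FEV₁ and PEF measured at the same visit. On the plan's own mechanism, lesion leads to muscle weakness, then to reduced inspiratory volume, then to weaker cough. PCF thus lies after MIP and FVC, and a model of either that contains PCF conditions on a consequence of its outcome. For MEP, FEV₁ and PEF the documents do not state an order, but PCF shares their causes, and conditioning on it removes part of the same signal.

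Three things are at stake in these secondary models. The coefficients for lesion level, AIS grade, partial ventilation and training would no longer be total effects and would be pulled toward zero. The PCF coefficient could be reported as a determinant of lung function when it is largely another reading of it. And PCF would have no model as an outcome, although the plan measures and describes it under the secondary endpoints.

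**Working it through.** The plan states no figure on this point, so there is none to reproduce. The check asks how much of a lesion effect survives when PCF is added.

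**Inputs.** The roles and timing come from sections 3.1, 5.2, 7, 7.2, 7.3 and 8.3.2 as set out above. The correlations are not in the documents and are assumed over wide ranges:

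- a = correlation of lesion (or ventilation, or training) with underlying respiratory function R: 0.3 to 0.7
- c = correlation of R with PCF: 0.3 to 0.95
- b = correlation of R with the modelled lung parameter Y; it cancels below

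**Formula.** With L the lesion variable and P the PCF, the standardised coefficient of L adjusted for P is

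(r_LY − r_YP × r_LP) / (1 − r_LP²).

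Under the chain L → R → (Y, P), r_LY = ab, r_LP = ac and r_YP = bc. The adjusted coefficient is ab(1 − c²)/(1 − a²c²) against ab unadjusted, so

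share retained = (1 − c²)/(1 − a²c²).

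If PCF is a direct consequence of Y (b = 1), the formula is the same. Half the effect is lost at c = √[0.5/(1 − 0.5a²)].

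**Example.** For a = 0.5 and c = 0.8: (1 − 0.64)/(1 − 0.25 × 0.64) = 0.36/0.84 = 0.43, a loss of 57%.

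**Share retained:**

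| a | c = 0.3 | 0.5 | 0.7 | 0.8 | 0.9 | 0.95 | c at which half is lost |
|---|---|---|---|---|---|---|---|
| 0.3 | 0.92 | 0.77 | 0.53 | 0.38 | 0.20 | 0.11 | 0.72 |
| 0.5 | 0.93 | 0.80 | 0.58 | 0.43 | 0.24 | 0.13 | 0.76 |
| 0.7 | 0.95 | 0.85 | 0.67 | 0.52 | 0.32 | 0.17 | 0.81 |

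The loss runs from about 5% (a = 0.7, c = 0.3) to about 89% (a = 0.3, c = 0.95). A simulation with 400,000 subjects at a = 0.5 gave 0.80, 0.58 and 0.24 for c = 0.5, 0.7 and 0.9, both with a shared cause and with PCF directly downstream of Y.

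**Without the chain.** If the three correlations are set freely, the answer is more sensitive still. Take r_LY 0.5–0.6, r_YP 0.6–0.8 and r_LP 0.4–0.6:

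- mildest corner: (0.60 − 0.6 × 0.4)/(1 − 0.16) = 0.429 against 0.60, a loss of 29%
- strongest corner: (0.50 − 0.8 × 0.6)/(1 − 0.36) = 0.031 against 0.50, a loss of 94%

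Outside those ranges even the direction can change. With r_LY = 0.6, r_LP = 0.6 and r_YP = 0.3 the coefficient rises slightly: (0.60 − 0.18)/0.64 = 0.656, or 1.09 times 0.60. Attenuation is therefore certain under the chain that section 3.1 supports, but not for every conceivable set of correlations.

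**The case against.** The strongest reply is that the plan is open. The predictors only 'include' PCF, multiple regression is only anticipated, and nothing says that all main predictors enter one model. The modelling strategy is still to be defined with causal-diagram software, mediation analysis is foreseen, and univariable models will give lesion effects without PCF. Further, no aim in section 4.1 and no paper in section 10.1 concerns the determinants of lung function.

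Much of this stands. The covariate set is not final and the stakes are limited. But the safeguards do not remove a variable that is named as an exposure:

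- An open list allows additions; it does not take PCF out.
- The causal-diagram sentence stresses extraneous and confounding variables in estimating predictor effects, PCF being one of those predictors. No diagram is given.
- Mediation concerns variables between predictor and outcome. On the section 3.1 account PCF comes after inspiratory strength and volume.
- Univariable models omit PCF, but also age, gender and time since injury. No confounder-adjusted model without PCF is named.

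A reader might infer more than the documents support, in three ways. One is that lesion and ventilation effects will be largely adjusted away; without documented correlations or a final model this cannot be said. Another is that PCF results from all five parameters; section 3.1 supports this for inspiratory strength and volume, not for MEP, FEV₁ or PEF. The third is that PCF should also leave the model of pneumonia determinants. Section 3.1 ties reduced cough capacity to a higher pneumonia risk, and section 7.2 wants PCF as an additive marker, so its use there is legitimate.

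**Conclusion.** The point holds for the secondary lung-function models. As worded, the plan makes PCF a main predictor of same-visit measures from which it follows (MIP, FVC) or with which it shares causes (MEP, FEV₁, PEF), and leaves it out of the modelled outcomes. The inconsistency in its role does not depend on any assumed number.

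The direction of the bias, toward zero, rests on the causal chain in section 3.1. Its size rests on assumed correlations and cannot be judged from the plan: it could be negligible or could remove most of the effect. The primary ROC analysis, the pneumonia models and the sample size are not touched.

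**What to change.** Make two edits in section 8.3.2 (Advanced regression modelling):

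1. In the paragraph on predictors, state that PCF is not a predictor in the models of MIP, MEP, FVC, FEV₁ and PEF. If its relation to them is of interest, report it in a separate analysis labelled as association, or as mediation where a stated causal diagram places PCF between predictor and outcome.
2. In the paragraph on secondary outcomes, add PCF to the lung parameters to be modelled.

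Leave PCF available as a predictor or additive marker for pneumonia.

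The cost is wording plus one further regression on data already collected at T1 to T4. No visit, measurement or recruitment figure changes.
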